8.2. Definitions

8.2.1. Adverse Event (AE)

An adverse event is any untoward medical occurrence in a clinical study subject administered a medicinal (investigational or non-investigational) product. An adverse event does not necessarily have a causal relationship with the treatment. An adverse event can therefore be any unfavorable and unintended sign

(including an abnormal finding), symptom, or disease temporally associated with the use of a medicinal (investigational or non- investigational) product, whether or not related to that medicinal (investigational or non-investigational) product. (Definition per International Conference on Harmonisation [ICH])

This includes any occurrence that is new in onset or aggravated in severity or frequency from the baseline condition, or abnormal results of diagnostic procedures, including laboratory test abnormalities.

8.2.2. Serious Adverse Event (SAE)

A serious adverse event based on ICH and EU Guidelines on Pharmacovigilance for Study drugs for Human Use is any untoward medical occurrence that at any dose:

- Results in death. (Note: death for any reason will be reported as a serious adverse event.)
- Is life-threatening. (The subject was at risk of death at the time of the event. It does not refer to an event that hypothetically might have caused death if it were more severe.)
- Requires inpatient hospitalization or prolongation of existing hospitalization
- Results in persistent or significant disability/incapacity
- Congenital anomaly/birth defect
- Suspected transmission of any infectious agent via a study drug
- Serious Infections
- Serious systemic hypersensitivity reactions
- Suicidality
- Cardiovascular events
- Medically important*

*Medical and scientific judgment should be exercised in deciding whether expedited reporting is also appropriate in other situations, such as important medical events that may not be immediately life threatening or result in death or hospitalization but may jeopardize the subject or may require intervention to prevent one of the other outcomes listed in the definition above. These should usually be considered serious.

8.2.2.1. Hospitalization

For reports of hospitalization, it is the sign, symptom or diagnosis which led to the hospitalization that is the serious event for which details must be provided.

Any event requiring hospitalization or prolongation of hospitalization that occurs during the study must be reported as a serious adverse event, except hospitalizations for the following:

- Hospitalizations not intended to treat an acute illness or adverse event (e.g., social reasons such as pending placement in long-term care facility)
- Surgery or procedure planned before entry into the study. [Note: Hospitalizations that were planned before the start of data collection and where the underlying condition for which the hospitalization was planned has not worsened will not be considered serious adverse events. Any adverse event that results in a prolongation of the originally planned hospitalization is to be reported as a new serious adverse event.]
- For convenience the investigator may choose to hospitalize the subject for the duration of the treatment period.

8.2.2.2. Life-Threatening Conditions

The cause of death of a subject in a study within 30 days of the last dose of study drug, whether or not the event is expected or associated with the study drug, is considered a serious adverse event.

Important medical events that may not result in death, be life-threatening, or require hospitalization may be considered serious when, based upon appropriate medical judgment, they may jeopardize the participant and/or participant may require medical or surgical intervention to prevent one of the outcomes listed in this definition. Examples of such medical events include:

- Allergic bronchospasm requiring intensive treatment in an emergency room or at home,
- Blood dyscrasias or convulsions that do not result in in-patient hospitalization, or
- The development of drug dependency or drug abuse.

8.2.3. Adverse Events of Special Interest

Adverse events of special interest are events that the COMPANY is actively monitoring as a result of a previously identified signal (even if non-serious). No adverse events of special interest will be collected for this study.

8.2.4. Individual Case Safety Report (ICSR)

A valid ICSR will contain the four minimum criteria requred to meet regulatory reporting requirements.

- an identifiable subject (but not disclosing personal information such as the subject's name, initials or address)
- an identifiable reporter (investigational site)
- a Janssen study drug
- an adverse event, outcome, or certain special situations

The minimum information required will be:

- suspected Janssen study drug (doses, indication)
- date of therapy (start and end date, if available)
- batch or lot number, if available
- subject details (subject ID and country)
- gender
- age at AE onset
- reporter ID
- adverse event detail (AE verbatim in English), onset date, relatedness, causality, action taken, outcome, (if available)
- Janssen protocol ID

8.2.5. Product Quality Complaint (PQC)

A product quality compliant is defined as any suspicion of a product defect related to a potential quality issue during manufacturing, packaging, release testing, stability monitoring, dose preparation, storage or distribution of the product, or delivery system. Not all PQCs involve a subject. Lot and batch numbers are of high significance and need to be collected whenever available.

Examples of PQC include but not limited to:

- Functional Problem: e.g., altered delivery rate in a controlled release product
- Physical Defect: e.g. abnormal odor, broken or crushed tablets/capsules
- Potential Dosing Device Malfunction: e.g., autoinjector button not working, needle detaching from syringe
- Suspected Contamination

Suspected Counterfeit

8.2.6. Unanticipated Problems (UP)

The Office for Human Research Protections (OHRP) considers UPs involving risks to participants or others to include, in general, any incident, experience, or outcome that meets all of the following criteria:

- Unexpected in terms of nature, severity, or frequency given (a) the research procedures that are described in the Tremfya package insert; and (b) the characteristics of the participant population being studied;
- Related or possibly related to participation in the research ("possibly related" means there is a reasonable possibility that the incident, experience, or outcome may have been caused by the procedures involved in the research); and
- Suggests that the research places participants or others at a greater risk of harm (including physical, psychological, economic, or social harm) than previously known or recognized.

This study will use the OHRP definition of UP.

8.3. Adverse Event Assessment and Follow-Up

The occurrence of an UP, AE or SAE may come to the attention of study personnel during study visits and interviews of a study participant presenting for medical care, or upon review by the PI. All AEs including local and systemic reactions not meeting the criteria for SAEs will be captured on the appropriate eCRF. Information to be collected includes event description, time of onset, clinician's assessment of severity, seriousness, expectedness, relationship to study product (assessed only by those with the training and authority to make a diagnosis), and date of resolution/stabilization of the event. All AEs occurring while on study must be documented appropriately regardless of relationship. All AEs will be followed to adequate resolution.

Any medical condition that is present at the time that the participant is screened will be considered as baseline and not reported as an AE. However, if the study participant's condition deteriorates at any time during the study, it will be recorded as an AE.

Changes in the severity of an AE will be documented to allow an assessment of the duration of the event at each level of severity to be performed. AEs characterized as intermittent require documentation of onset and duration of each episode.

At each study visit, the Investigator will inquire about the occurrence of AE/SAEs since the last visit. Events will be followed for outcome information until resolution or stabilization.

The Investigator will record all reportable events with start dates occurring any time after informed consent is obtained until the week-36 follow-up study visit. Any SAE that occurs after treatment with alternative therapy will be reported only if the Investigator or current treating physician has assessed the SAE as related to the study treatment.

All serious adverse events that have not resolved by the end of the study, or that have not resolved upon discontinuation of the subject's participation in the study, will be followed until any of the following occurs:

- The event resolves
- The event stabilizes
- The event returns to baseline, if a baseline value/status is available
- The event can be attributed to agents other than the study drug or to factors unrelated to study conduct

• It becomes unlikely that any additional information can be obtained (subject or health care practitioner refusal to provide additional information, lost to follow-up after demonstration of due diligence with follow-up efforts)

All follow-up information for serious adverse events or AEs of special interest and special situations that are not resolved at the end of the study or by the time of patient withdrawal will be reported directly by the PI, within 24 hours becoming aware, to Janssen Scientific Affairs using Janssen Scientific Affairs' Serious Adverse Event Report.

All available clinical information relevant to the evaluation of a related SAE, Adverse Events of Special Interest, serious ADR or special situation is required.

- The PI is responsible for ensuring that these cases are complete and if not are promptly followedup. A safety report is not considered complete until all clinical details needed to interpret the case are received. Reporting of follow-up information should follow the same timeline as initial reports.
- Copies of any and all relevant extraordinary (not including routine initial or follow-up ICSR submission) correspondences with regulatory authorities and ethics committees regarding any and all serious adverse events, irrespective of association with the study drug, will be provided to Janssen Scientific Affairs within 24 hours of such report or correspondence being sent to applicable health authorities.

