6.4.2. Prohibited Medications, Treatments, and Procedures

The following therapies will not be permitted during the course of the study:

- Treatment with systemic therapy intended to treat PRP within the washout period specified in the exclusion criteria, including prednisone, methotrexate, cyclosporine, acitretin, and injectable biologic therapies. These medications could have a negative safety impact on the subjects enrolled and confound the results of the study.
- New use of topical steroids or increased potency of topical steroids after enrollment
- Live vaccines
- Phototherapy within the 4-week washout period

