6.4.3. Permitted Medications, Treatments, and Procedures

The following medications will be permitted during the course of the study:

- Topical emollients
- Topical steroids may be maintained at levels used prior to enrollment, decreased, or discontinued, but potency and weekly grams used may not be increased
- Non-live vaccines (such as the non-live annual influenza vaccine, non-live herpes zoster vaccine (Shingrix), rabies, or tetanus) and/or emergency vaccines are allowed
- Acetaminophen, aspirin, or ibuprofen as needed
- Subjects will maintain their usual medication regimen for other concomitant diseases throughout
 the study unless specifically excluded in the protocol. Subjects taking concomitant medications
 should be on a stable dose throughout the study, unless changes need to be made for an AE or
 for appropriate medical management. If a medication is changed, the changed and reason for it
 will be documented. Additional systemic drugs are to be avoided during the study, unless

required to treat an AE. Other medications may be allowed, if approved by the investigator. Any changes in medications should be discussed with the investigator. Subjects should be instructed to consult the investigator or other appropriate study personnel at the site before taking any new medications or supplements. All therapies (prescription, over-the-counter, vitamins, herbal supplements, vaccines) will be recorded in the eCRF as outlined in the Study Procedures.

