7.2.3. Exploratory Endpoint Analyses

- Sustained remission at week-36, measured by the mean change in PASI score from week-24 to week-36, will be analyzed for statistical significance using a paired, two-tailed Student's t-test.
- Treatment response, as measured by PASI 50, will be stratified by CARD14 germline mutations. The proportion of subjects with a PASI 50 response with and without CARD14 mutations will be reported and compared for statistical significance using an unpaired, two-tailed Student's t-test.
- Epithelial expression of CARD14 will be assessed qualitatively by a trained dermatopathologist who is blinded to the biopsy collection time (before or after therapy).
- The gene expression level from the tissue biopsy, before, 4 weeks, and 24 weeks after treatment, will be analyzed for statistical significance using a pared, two-tailed Student's t-test and also compared with normal and psoriatic skin using a two-tailed, two-sample Student's t-test with unequal variance adjusted for multiple comparisons.
- The cytokine level from serum before, 4 weeks, and 24 weeks after treatment, will be analyzed for statistical significance using a pared, two-tailed Student's t-test and also compared with normal and psoriatic serum using a two-tailed, two-sample Student's t-test with unequal variance adjusted for multiple comparisons.

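### Sections 6.4.2, 6.4.3 and 8.3 do not agree on other PRP therapy between week 0 and week 36, and Section 7.2 has no rule for PASI scored after such therapy

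*Combined protocol and SAP*

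**What the plan says.** **Rules on other therapy.** Section 6.4.2 introduces its list as treatments barred while the study runs. The first item is "Treatment with systemic therapy intended to treat PRP within the washout period specified in the exclusion criteria", with prednisone, methotrexate, cyclosporine, acitretin and injectable biologics as examples. The last is "Phototherapy within the 4-week washout period". Section 4.2 counts the washout back from baseline. The reason given in 6.4.2 for barring the systemic drugs is that they "could have a negative safety impact on the subjects enrolled and confound the results of the study".

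Section 6.4.3 says "Additional systemic drugs are to be avoided during the study, unless" they are needed for an adverse event, and adds "Other medications may be allowed, if approved by the investigator". Neither sentence makes an exception for PRP treatment.

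Section 8.3 takes conditions present at screening as baseline, but "if the study participant's condition deteriorates at any time during the study, it will be recorded as an AE". It also contains an SAE-reporting rule: "Any SAE that occurs after treatment with alternative therapy will be reported only if" the event is assessed as related to study treatment.

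**Analysis.** Section 7.2.1 compares baseline and week-24 PASI with a paired two-sided t-test. Section 7.2.3 does the same for "Sustained remission at week-36, measured by the mean change in PASI score from week-24 to week-36". Neither mentions scores taken after other PRP therapy.

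**Safeguards.** The week-24 visit is brought forward if study drug is stopped or the subject withdraws before then (Sections 5.2, 8.7.1, 8.7.2). The week-36 visit is brought forward only on withdrawal after week 24 (Section 5.2). Concomitant medications are asked about at every visit (Section 6.4.1).

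**The concern.** An investigator cannot tell from these sections whether a subject whose PRP worsens may start another PRP treatment and remain in the study. If some do, the analysis has no instruction for their later scores, and the recorded PASI goes into the test.

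The resulting bias has a direction. Subjects who relapse are the likeliest to start something else. If it works, their PASI falls again, and the mean change from week 24 to week 36 moves towards zero. This endpoint is meant to separate remission from relapse, and a change near zero is what would be read as remission. The bias therefore favours guselkumab.

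From week 24 to week 36 no study drug is given (the last dose is at week 20) and Table 1 schedules no visit. Twelve weeks is long enough for another drug to act: Section 1.1 cites marked improvement in 90% of reported cases on a related biologic class, often 4 weeks after one injection.

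**Working it through.** **1. Setting the sections side by side**

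| Section | Taken literally |
|---|---|
| 6.4.2, heading | other PRP therapy barred throughout the study |
| 6.4.2, items | bar tied to a period that ends at baseline |
| 6.4.3 | systemic drugs possible for an adverse event; other drugs possible with approval |
| 8.3, deterioration | worsening of a baseline condition is an adverse event, so worsening PRP can meet the 6.4.3 exception |
| 8.3, SAE rule | presupposes that some subjects receive alternative therapy |
| 8.7.1, 8.7.2 | use of other PRP therapy is not a named reason to stop drug or withdraw |

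**2. The plan's own figure**

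Section 7.1 gives power 0.8031 for n = 10, mean change 8, SD 8, two-sided 0.05. The paired t-test has noncentrality (8/8)·√10 = 3.16 on 9 degrees of freedom, which gives 0.8031. The figure reproduces; at n = 15 it is 0.949. The sample size is not in question.

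**3. Week 36**

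The documents give no relapse rate and no frequency of other therapy, so these inputs are assumptions: n = 15 (the recruitment goal), true off-drug change from week 24 to week 36 normal with mean +4 and SD 6, and the k worst relapsers treated back exactly to their week-24 score (change 0).

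Reported mean = (15 × 4 − k × average rise of the k worst) / 15. The averages and rejection rates come from 400,000 simulated trials.

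| k | Average rise of the k worst | Reported mean rise | Chance of a significant result |
|---|---|---|---|
| 0 | – | 4.0 | 67% |
| 1 | 14.42 | (60 − 14.42)/15 = 3.0 | 55% |
| 2 | 12.95 | (60 − 25.90)/15 = 2.3 | 42% |
| 3 | 11.86 | (60 − 35.58)/15 = 1.6 | 31% |
| 4 | 10.97 | (60 − 43.88)/15 = 1.1 | 22% |

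The k = 0 row agrees with the exact calculation: noncentrality (4/6)·√15 = 2.58 on 14 degrees of freedom gives 0.67.

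Two variants show the range for n = 15, borrowing the planning values as a rise of 8 with SD 8:
- k worst reset to zero change: 95% with none, then 90%, 83%, 73%, 61% for k = 1 to 4.
- k subjects chosen without regard to relapse, each lowered by 8: 95%, then 91%, 85%, 77%, 69%.

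**4. Week 24**

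If k of n subjects have a score improved by R points through other therapy, the mean shifts by kR/n. For n = 15 and R = 16 (assumed), that is 1 × 16/15 = 1.1 points for one subject, 2.1 for two and 3.2 for three. With R from 8 to 24, one subject shifts it by 0.5 to 1.6. If guselkumab had no effect (SD 8, R = 16), the chance of a significant improvement would rise from 2.5% to about 4%, 8%, 14% and 24% for k = 1 to 4.

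**The case against.** The intent of Section 6.4.2 can be defended. Its heading bars these treatments during the study, and its confounding rationale makes sense only for on-study use. The washout wording may be loose drafting, and 6.4.3 does tell subjects to avoid additional systemic drugs. The adverse-event route needs several steps that no single sentence states. This is fair, but the items still say what they say, and nothing excludes PRP therapy from the two exceptions.

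A reader might infer from Section 8.3 that the protocol permits or expects a move to alternative therapy. It does not go that far. The sentence governs SAE reporting, does not say the therapy is for PRP, and would also fit a subject who has stopped study drug and is under another physician. The stronger conflict is 6.4.2 against 6.4.3 together with the deterioration sentence in 8.3.

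A reader might also infer that the plan declares PASI after other therapy to be guselkumab response. It makes no such statement; the result follows from silence.

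The primary endpoint is better protected than week 36. The early week-24 visit leaves exposed mainly subjects who add therapy while staying on drug, or whose early visit is missed or comes after the new therapy has started.

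Finally, this is a small open-label pilot, and the week-36 test is placed among the exploratory analyses in 7.2.3 (though 3.2.3 lists it as secondary). That limits the stakes. But with 10 to 15 subjects, one or two such cases can change how the result reads.

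**Conclusion.** The point holds as an inconsistency to be reconciled together with a missing analysis rule. By default, scores taken after other PRP therapy enter both paired t-tests, contrary to the protocol's own warning about confounding. The main exposure is the week-36 remission result; the week-24 exposure is narrower.

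Under the assumed rise of 4 (SD 6) in 15 subjects, one to four treated relapsers reduce the reported rise to between 3.0 and 1.1, and the chance of detecting it from 67% to between 55% and 22%. The four-subject case is the extreme of that range and should not be read as the expected effect. All these sizes depend on assumed numbers of affected subjects and on full return to the week-24 score; the documents supply neither.

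**What to change.** 1. **Reconcile Sections 6.4.2, 6.4.3 and 8.3** on other PRP therapy between week 0 and week 36. The clinical team decides the rule; this review takes no view on it.
2. **Week 24 (Section 7.2.1).** For a subject who starts other PRP therapy before the week-24 score, use the last PASI before that start. After baseline, scheduled scores exist at weeks 4, 8, 12 and 20.
3. **Week 36 (Section 7.2.3).** Do not carry the week-24 score forward. With no scheduled visit in between, that sets the change to zero, which is the value assigned to treated relapsers in the illustration and so reproduces the bias. Instead, report the number and proportion who started other PRP therapy after week 24. Beside the mean change, report a defined proportion in sustained remission in which these subjects count as not in remission. Use a PASI taken before the new therapy where one exists, for example by bringing the week-36 visit forward, as Section 5.2 already does on withdrawal.
4. **Timing.** Fix these rules before outcome data are examined, since Section 7.2 has the investigator analysing data throughout.

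**Cost.** Text corrections, one analysis rule, one added proportion with its definition, and possibly some early visits. Medications are already recorded at each visit; start dates are needed. The remission figure may look less favourable.

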8. SAFETY

8.1. Specification of Safety Parameters

As the sponsor of the Study, OHSU and the PI shall be solely responsible for complying, within the required timelines, any safety reporting obligation to competent Health Authorities, IRB and any participating (co or sub) investigators, as defined in applicable laws and regulations. For the purposes of this protocol, safety data includes adverse events, product quality complaints (PQCs), and special situations including pregnancies. Safety assessments will be based on medical review of adverse events and the results of safety evaluations at specified time points as described in Section 5.1 Study Visit Procedures. Any clinically significant adverse events persisting at the end of treatment visit will be followed by the Investigator until resolution/stabilization or death, whichever comes first.

OHSU and the PI will provide safety information to Janssen Scientific Affairs on adverse events, special situations including pregnancies and product quality complaints as defined within this protocol.

This Study has been designated as an interventional study. As such, all adverse events for Janssen Study drugs regardless of causality and special situations excluding those from subjects not exposed to a Janssen Study drug and product quality complaints with or without an adverse event as described in this Protocol will be reported from the time a subject has signed and dated an Informed Consent Form (ICF) until completion of the subject's last study-related procedure (which may include contact for follow-up safety). Serious adverse events will be reported up to week-36 (16 weeks after the last dose of study drug).

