8.4. Reporting Procedures

All adverse events and special situations, whether serious or non-serious, related or not related, following exposure to the study drug will be documented by the investigator and recorded in the eCRF and in the subject's source records. Investigators will record in the eCRF their opinion concerning the relationship of the adverse event to the study drug. All (serious and non-serious) adverse events reported for the study drug will be followed-up in accordance with clinical practice.

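### Section 8.3 makes SAE reporting after alternative therapy depend on a causality judgement, against the unconditional rules in 8.1, 8.2.2 and 8.4.2.3, and lets follow-up of some unresolved SAEs end on attribution

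*Combined protocol and SAP*

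**What the plan says.** Two parts of section 8.3 matter here.

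**Reporting.** Directly after setting a recording period from consent to week 36, section 8.3 adds that an SAE arising once alternative therapy has begun "will be reported only if the Investigator or current treating physician has assessed the SAE as related to the study treatment". The general rules carry no such condition:

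- Section 8.1 requires reporting of "all adverse events for Janssen Study drugs regardless of causality and special situations", from consent to the subject's last study procedure. It adds: "Serious adverse events will be reported up to week-36 (16 weeks after the last dose of study drug").
- Section 8.2.2 notes that "death for any reason will be reported as a serious adverse event".
- Section 8.4.2.3 sends any SAE to the manufacturer within 24 hours of awareness.
- Section 8.4 is a recording rule: "All adverse events and special situations, whether serious or non-serious, related or not related, following exposure to the study drug will be documented", in the eCRF and in the source records.

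**Follow-up.** For SAEs still unresolved at the end of the study, or when a subject's participation is discontinued, section 8.3 lists conditions, any one of which ends follow-up. One is: "The event can be attributed to agents other than the study drug or to factors unrelated to study conduct". Earlier in the same section every AE is to be followed until adequately resolved. Section 8.1 has clinically significant AEs that persist at the end-of-treatment visit followed until they resolve or stabilize, or the subject dies.

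**The concern.** Whoever completes the SAE form needs one rule. For an SAE after a change of therapy, section 8.3 asks for a causality opinion first and allows no report if that opinion is negative. Sections 8.1, 8.2.2 and 8.4.2.3 ask for the report whatever the opinion.

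The condition falls on subjects who have gone on to other therapy, where guselkumab exposure and the new agent may overlap and attribution of a single case is least secure. Section 1.1 says that there is no published systematic trial in PRP and no published report of IL-23p19-targeted therapy in this disease. There is thus little background against which an individual case could confidently be called unrelated. At stake is prompt notice of serious events to the manufacturer, and follow-up of serious events to a known outcome.

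**Working it through.** No sample size, power or error-rate figure is involved, so the check sets the sections side by side.

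**Step 1: can the situation occur within the reporting window?** Section 8.7.1 says that stopping study drug does not automatically withdraw the subject. Section 6.4.2 does not permit other systemic PRP therapy during the study, but no section says that starting it ends participation. The sentence in 8.3 itself presupposes that alternative therapy may occur, and the protocol does not define the term. The last scheduled dose is at week 20 (section 6.2) and the SAE limit is week 36, so 36 − 20 = 16 weeks, which agrees with section 8.1. Because 8.1 names week 36 as the limit, a subject still in the study whose last dose was at week 4 is covered for 36 − 4 = 32 weeks. The situation is possible both after early discontinuation and after the week-20 dose.

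**Step 2: apply each reporting rule to an SAE after alternative therapy, before week 36, in a subject still in the study.**

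| Judgement | 8.3 conditional sentence | 8.1 | 8.4.2.3 | 8.2.2, if fatal |
|---|---|---|---|---|
| Investigator: related | Report | Report | Report in 24 h | Report |
| Only the treating physician: related | Report | Report | Report in 24 h | Report |
| Neither: related | Do not report | Report | Report in 24 h | Report |

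The rules differ only in the last row, and there they cannot all be followed. A fatal event that both physicians consider unrelated is the plainest case: 8.2.2 requires a report and 8.3 excludes it.

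**Step 3: what happens to a last-row event elsewhere in the protocol?** Section 8.3 also requires every on-study AE to be documented whatever its relationship, and section 8.4 puts it in the eCRF. Section 8.5 has the principal investigator review AEs in real time and the data at least monthly, and provide all AEs, serious and non-serious, to the manufacturer in report format. Section 8.4.2 requires a full AE summary in the final report. The event is therefore recorded, reviewed and eventually passed on. What 8.3 puts in doubt is the 24-hour report. The semi-annual listing in 8.4.2 need not reveal the omission, because it is built from SAEs that the manufacturer has already received.

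**Step 4: apply each follow-up rule to an SAE that is unresolved and not stabilized at study end and is attributed to another agent.**

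- Stop list in 8.3: follow-up may end.
- General sentence in 8.3: follow-up continues to adequate resolution.
- Section 8.1, if the event is clinically significant and was present at the end-of-treatment visit: follow-up continues to resolution, stabilization or death.

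The stop list covers SAEs only, and non-serious AEs have no attribution exit. On the text, a serious event could be released from follow-up sooner than a non-serious one.

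**The case against.** A fair defence runs as follows. The sentence in 8.3 can be read as a specific exception to a general rule. It restricts what is reported, not what is recorded. A related judgement by either physician is enough to trigger a report. Sections 6.4.2 and 6.4.3 discourage other systemic therapy, so few subjects should be affected. The stop list concerns only SAEs open at study end or at discontinuation of participation.

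Most of this stands, and it limits the point. The exception reading does not remove the conflict: 8.1, 8.2.2 and 8.4.2.3 do not refer to an exception, the rule on deaths is itself specific and unconditional, and 8.3 does not say to whom a report would be withheld.

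A reader might infer three stronger things that the documents do not support:

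- *The SAE count will be biased downward.* The wording about recording reportable events in 8.3 is loose, but 8.4 is clear that every AE enters the eCRF, related or not. The tabulated count need not change.
- *Cases are hidden from the investigator's safety review or never reach the manufacturer.* Sections 8.5 and 8.4.2 provide for review, for reports covering all AEs, and for a complete final summary.
- *The attribution stop breaches the rule in 8.1 covering "all adverse events for Janssen Study drugs regardless of causality".* That rule governs reporting. The stop list conflicts with the follow-up rules in 8.1 and 8.3 instead.

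**Conclusion.** The contradiction is real. For an SAE after alternative therapy that neither physician calls related, 8.3 cannot be reconciled with 8.1 and 8.4.2.3, or with 8.2.2 if the event is fatal. The consequence is a possible missed 24-hour report inside the week-36 window. The separate follow-up conflict is narrower and applies only to SAEs unresolved at study end or at discontinuation of participation.

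The size cannot be put in numbers: the documents give neither an expected SAE rate nor an expected number of subjects starting other therapy, and any figure would be invented. The conclusion assumes that the word reported in 8.3 includes the expedited report to the manufacturer, and that a subject who starts other therapy may remain in the study, which no section rules out. The effect is confined to safety reporting and follow-up; the primary PASI analysis and its power are unaffected. It merits correction because the change is small and the present text gives site staff opposite instructions.

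**What to change.** 1. Delete the conditional sentence from 8.3, so that 8.1, 8.2.2 and 8.4.2.3 govern every SAE up to week 36.
2. Record any alternative therapy and its start date on the SAE form, with a short definition of the term, and tabulate SAEs before and after that date. The causality opinion is then kept as information and no longer acts as a filter.
3. Remove attribution to other agents or unrelated factors from the SAE stop list in 8.3, and align the rest of that list with the follow-up rules in 8.1 and 8.3.

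The cost is a protocol wording amendment, one or two added fields on the form, and a few extra SAE forms and some further follow-up for events that prove unrelated. No visit, treatment rule or efficacy analysis changes.
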